#### Best Corrected Visual Acuity (BCVA)

BCVA will be summarized in logMAR units by treatment for the screening (pre-dose) and Day 1 (post-dose), using a number of observations, mean, standard deviation, minimum, median, and maximum values. The analysis will be based on the safety population defined in Section 3.1.

For both study eye and non-study eye, changes in BCVA at post-dose from screening (pre-dose) will be analyzed for differences between AG-920 and placebo groups, using analysis of covariance (ANCOVA), with the pre-dose measurement as the covariate.

#### Biomicroscopy (Slit-Lamp)

Total severity scores of Biomicroscopy (Slit-Lamp of seven items on grading scale, including lid erythema, lid edema, conjunctiva hyperemia, conjunctiva edema, corneal edema, anterior chamber cells, and anterior chamber flare) will be summarized by treatment for the screening (pre-dose) and Day 1 (post-dose), using a number of observations, mean, standard deviation, minimum, median, and maximum values. The analysis will be based on the safety population defined in Section 3.1.

For both study eye and non-study eye, changes in the total severity score at post-dose from screening (pre-dose) will be analyzed for differences between AG-920 and placebo groups, using analysis of covariance (ANCOVA), with the pre-dose measurement as the covariate.

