1.2 Potential Risks and benefits to human subjects

Minimal risks are expected with AG-920.

Expected risks for subjects may include a temporary mild to moderate stinging or burning sensation upon instillation of the investigational medical product (IMP). Temporary mild hyperemia may also occur following instillation. For any additional information on AG-920 use, please refer to the [Investigator's Brochure](#).

As this study is to be conducted in healthy subjects, there is no anticipated benefit other than the possibility that a subject's participation in the present study may help others in the future to have more options for local anesthesia before ophthalmic procedures.

Adverse events (AEs) not reported in previous clinical trials but present among subjects in this clinical trial will be communicated to Investigators and to ethics committees or Institutional Review Board (IRBs) in accordance with local regulations.

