4.2 Subject exclusion criteria

Subjects who meet any of the following exclusion criteria are ineligible for this study:

1. Have participated in an investigational study (drug or device) within the past 30 days.
2. Have a contraindication to local anesthetics, [REDACTED] or any component of the IMP.
3. Have known decreased corneal or conjunctival sensitivity (e.g., sequelae of herpetic eye disease, corneal graft) or a diagnosed corneal pathology which might lead to decreased sensitivity.
4. Have had ocular surgery (intraocular, refractive, extraocular muscles, eyelid) or general surgery in either eye within the past 90 days (Note: dental restorative work allowed)
5. Have had an intravitreal injection in either eye within 14 days of randomization.
6. Have ocular surface disease requiring punctal plugs.
7. Evidence of any current ocular inflammation.
8. Subject who must wear contact lenses on Study Day 1 (Visit 2).
9. Are currently using, or used within the past 30 days, a systemic opioid or opiate analgesic or topical Non-steroidal Anti-Inflammatory Drug (NSAID).
10. Subject who cannot withhold their intermittent over-the-counter (OTC) artificial tear lubricant products for one hour preceding or following study medication.
11. Any condition, including alcohol or drug dependency, that would limit the subject's ability to comply with the procedures of the protocol (per Investigator's judgment).
12. The subject or a close relative of the subject is the investigator or a sub-investigator, research assistant, pharmacist, study coordinator, or other staff directly involved in the conduct of the study.

Note: Given the approval status and preclinical safety information on the molecule, and low chance of systemic exposure, other than the negative urine pregnancy test, there is no restriction on women of child-bearing potential.

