6.4.3 Post Treatment and Pinch Test

- [REDACTED] forceps will be used to “pinch” the [REDACTED] conjunctiva of the study eye at the following timepoints. Details on the pinching method will be provided separately:
 - **20 seconds following complete dose administration** (second drop of IMP)
 - **40 seconds following dose administration**
 - **60 seconds following dose administration**
 - **5 minutes following dose administration**
- Immediately following EACH pinch test, subjects will be asked “Was that painful” “Yes” or “NO.” It should be explained to subjects that the feeling of pressure is NOT to be judged as pain. [REDACTED]
[REDACTED].

All subjects are pinched at 20, 40, 60 seconds and 5 minutes post dose. If the subject feels no pain at 5 minutes, the subject will be considered “anesthetized.” Pinching of anesthetized subjects will continue at 10 minutes and EVERY FIVE MINUTES for up to 30 minutes or until pain resumes. Once pain resumes, pinching is stopped.

If the subject experiences pain at 5 minutes, pinching will be concluded and this subject will be considered to NOT have reached anesthesia at 5 minutes.

Within 15-60 minutes after the last pinch test, the following examinations will be performed

- BCVA
- Perform slit lamp biomicroscopy and external eye exam
- Assess for adverse events
- Schedule Follow-up Phone Call between Day 2-5 (1-4 days following dosing).

Windows: Times will be measured to the nearest minute with the exception of the 20, 40 and 60 second time points. Those should be recorded to the second. Times up to 5 minutes post 2nd instillation should be followed. Investigators are allowed a window of \pm 1 minute at the 10 minute time point, and \pm 2 minutes at subsequent time points.

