9.4.7 Analysis of Safety

Slit lamp biomicroscopy and external eye exam measures will be summarized at each measured time point using discrete summary statistics.

Visual Acuity data will be summarized at each time point using both continuous summaries (Logarithmic Minimum Angle of Resolution, logMAR), including change from baseline, and discrete summaries, including change from baseline in the number of lines and the proportion of subjects with a worsening of ≥ 3 lines from baseline.

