### **2.9 Statistical Methods**

Unless specified otherwise, SAS® Version 9.0 or higher will be utilized to perform the statistical analyses of efficacy and safety measures.

Categorical variables will be summarized in general using frequencies and percentages, whereas continuous variables will be summarized in general using descriptive statistics of number of observations (n), mean, standard deviation (SD), minimum (Min), median, and maximum (Max).

In both data listings and CRF domain data tabulations, subject ID will consist of site number plus the subject screening number in the format of XXX-YYY, where XXX denotes the site number and YYY the subject's screening number within the site.

Hypothesis testing, unless otherwise indicated, will be performed at the 5% significance level. All p-values will be rounded to four decimal places; p-values less than 0.0001 will be presented as '<0.0001' in all tables. All group comparisons from analysis of variance (ANOVA) and/or analysis of covariance (ANCOVA) models will be based on Type III sums of squares. In the case of substantial non-normality, results from non-parametric tests will also be reported. All confidence intervals (CI) will be two-sided with 95% coverage.

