#### **5.5 Biomicroscopy and External Eye Exam**

Descriptive and inferential statistics of Biomicroscopy (Slit-Lamp) total severity score will be presented by treatment for the pre-dose (screening) and post-dose assessments and their changes in post-dose assessment from pre-dose in Table 6.1.1 for the study eye.

Descriptive and inferential statistics of Biomicroscopy (Slit-Lamp) total severity score will be presented by treatment for the pre-dose (screening) and post-dose assessments and their changes in post-dose assessment from pre-dose in Table 6.2.1 for the non-study eye.

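### The SAP's named slit-lamp tables give only a seven-item total score, not the discrete summaries the protocol calls for, so they cannot show which sign changed or how severely

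*SAP*

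**What the plan says.** Protocol 9.4.7 states: "Slit lamp biomicroscopy and external eye exam measures will be summarized at each measured time point using discrete summary statistics". It names no composite score and no test. Biomicroscopy is among the secondary endpoints in protocol section 2, and protocol 8.1 lists cornea, conjunctiva and anterior chamber as structures to be evaluated.

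The section on biomicroscopy in SAP 2.9.3 takes seven graded signs ("lid erythema, lid edema, conjunctiva hyperemia, conjunctiva edema, corneal edema, anterior chamber cells, and anterior chamber flare") and works with their total. It reports n, mean, SD, minimum, median and maximum at screening and post-dose. For each eye it then says that "changes in the total severity score at post-dose from screening (pre-dose) will be analyzed for differences between AG-920 and placebo groups", using ANCOVA with the pre-dose score as covariate.

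SAP 5.5 covers biomicroscopy and the external eye exam by its title, but its text is confined to the score: "Descriptive and inferential statistics of Biomicroscopy (Slit-Lamp) total severity score will be presented by treatment", in Table 6.1.1 for the study eye and Table 6.2.1 for the non-study eye.

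Protocol 1.2 names one expected effect that matches a scored sign: "Temporary mild hyperemia may also occur following instillation".

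**The concern.** The two documents describe different analyses of the same safety data, and the readable SAP text gives no reason for the change. The seven signs are not interchangeable: lid erythema and anterior chamber cells carry different meaning, and corneal edema can matter in a single subject. A total treats one grade on any of them as equal and lets a fall in one sign cancel a rise in another.

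At stake is what the comparative safety tables can tell a reader. If the SAP text is followed as written, they would not answer how many subjects per arm developed hyperemia, or whether any developed corneal or anterior chamber signs.

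**Working it through.** The documents give no figure for the slit-lamp analysis, so there is none to reproduce. The sample size is 60 per arm (SAP 2.5). The grading scale, the item SDs and the expected changes do not appear in the readable text, so every grade and SD below is an assumption.

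**1. Protocol against SAP.**

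| | Protocol 9.4.7 | SAP 2.9.3 and 5.5 |
|---|---|---|
| Unit | Individual measures | Total of seven signs |
| Statistics | Discrete | Mean, SD, median, range |
| Comparison | None named | ANCOVA on change |
| External eye exam | Included | Only the two lid signs in the score |

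**2. Two different safety profiles, one table.** Assume all screening totals are 0 and the scale reaches grade 3.
- Arm A: 3 of 60 subjects have +3 on corneal edema.
- Arm B: 3 of 60 subjects have +1 on each of hyperemia, conjunctival edema and lid erythema.

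In both arms the mean change is 3 × 3/60 = 0.15. The variance is (3 × 9 − 60 × 0.15²)/59 = 25.65/59 = 0.435, so the SD is 0.66. The minimum is 0, the median 0 and the maximum 3. Every statistic planned for the total is the same, and the between-arm difference is 0. An item-level table would separate the arms at once.

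**3. Does the sum lose sensitivity?** Suppose the drug shifts hyperemia by d SDs. Let the other six signs be independent, unaffected by the drug, and each have an SD of r times the hyperemia SD. The standardized effect on the sum is d/√(1 + 6r²). Take d = 0.51, which gives 80% power at 60 per arm for hyperemia alone.

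| r | Effect kept | Power of the sum | n per arm for 80% |
|---|---|---|---|
| 0 | 100% | 80% | 60 |
| 0.1 | 97% | 78% | 64 |
| 0.25 | 85% | 67% | 83 |
| 0.5 | 63% | 43% | 150 |
| 1 | 38% | 18% | 420 |

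The loss runs from none to severe, depending on r, and the documents do not fix r. Protocol 4.2 excludes subjects with "Evidence of any current ocular inflammation", which points towards low values for the inflammatory signs.

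**4. A few severe findings.** Let k of 60 AG-920 subjects have +3 on one sign, with none on placebo and all other scores 0. A t-test stands in for the ANCOVA.
- k = 1: the mean moves by 3/60 = 0.05, p = 0.319.
- k = 3: the mean moves by 0.15, with SE √(0.435/60) = 0.085 and t = 1.76, p = 0.081. Fisher's test on the counts gives 2 × C(60,3)/C(120,3) = 2 × 34,220/280,840 = 0.244.
- k = 4: the mean moves by 0.20, p = 0.042. Fisher's test gives 0.119.

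With quiet background items, then, the test on the sum gives the smaller p-value. What the total loses is the identity and grade of the finding.

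**5. Pinching.** All subjects are pinched 4 times by 5 minutes, and then: "Pinching of anesthetized subjects will continue at 10 minutes and EVERY FIVE MINUTES for up to 30 minutes or until pain resumes". That adds up to 5 (at 10, 15, 20, 25 and 30 minutes), for up to 9. At the response rates behind the sample size (40% and 15%), 0.40 × 60 = 24 AG-920 subjects and 0.15 × 60 = 9 placebo subjects would go on to further pinches. Conjunctival signs could therefore differ by arm for mechanical reasons (my inference). A total cannot separate these from corneal or anterior chamber signs.

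**The case against.** The strongest reply is that the item-level tables may already be planned. The SAP's lists of tables, listings and figures are redacted, and SAP 2.9 has a general rule: "Categorical variables will be summarized in general using frequencies and percentages". This stands to the extent that absence is not proven. But 2.9.3 and 5.5 are where the slit-lamp method is defined, and they give a different, specific method.

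A reader might infer that the sum necessarily dilutes a hyperemia effect, or that it would miss most real signals. The documents support neither. Dilution needs noisy other items. In an assumed scenario with 3 of 60 against 0 of 60 at +3 and trace findings on each item in 5% before and 10% after dosing, the test on the total reaches p < 0.05 in about 9% to 11% of simulated trials. With 1% and 2% background it is 15% to 17%. These rates follow from the assumed grades and background, and mostly show that three subjects in 60 are few. The scenario also uses grade 3, where protocol 1.2 expects mild hyperemia.

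A reader might also infer that a severe finding would be hidden. It would not vanish from the report. The tables print the maximum total, an abnormal sign can be recorded as an adverse event and tabulated by preferred term and eye, and all data are listed. These routes are real but partial: the maximum does not name the sign, adverse event tables depend on the investigator recording it as an event, and listings do not compare arms.

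**Conclusion.** The concern holds as a departure from the protocol and a loss of item-level information in the named comparative displays. The SAP text substitutes the mean and ANCOVA of a seven-sign total for discrete summaries. No named table gives the frequency by arm of hyperemia, of corneal or anterior chamber findings, or of external eye findings beyond the lid signs in the score.

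This conclusion rests on the readable text, and an item-level table in the redacted list would narrow it to a gap in 2.9.3 and 5.5. It does not rest on any power or detection figure, and none can be derived from the documents. The point concerns a safety display and leaves the primary efficacy result untouched.

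**What to change.** In SAP 2.9.3 and 5.5:
- Add item-level frequency tables and shift-from-screening tables for each of the seven signs, by arm and by eye.
- For each sign, give the number and percent of subjects worsening by at least 1 and by at least 2 grades, and state the grading scale beside the table.
- Add a summary of the external eye exam findings by arm and eye.
- Keep the total-score summary and ANCOVA as supplementary, with a sentence explaining why it was added to the protocol's discrete summaries.

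If the redacted table list already contains such tables, cite their numbers in both sections. The cost is a few more safety tables from data already collected. No new assessments are needed.

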#### **2.9.4 Other analysis**

The concomitant medications, including those for study eye and non-study eye, will be grouped into those taken pre-randomization and those taken post-randomization as well as those taken post-treatment, based upon the starting dates of the concomitant medication and the treatment.

Number and percent of subjects in the safety population who take pre-randomization concomitant medications will be reported. Number and percent of subjects in the safety population who take post-randomization concomitant medications will be reported by treatment and by study eye vs. non-study eye. Number and percent of subjects in the safety population who take post-treatment concomitant medications will be reported by treatment and by study eye vs. non-study eye.

### **3 STUDY POPULATION**

#### **3.1 Definition of Subject Populations**

All subjects who have the randomization procedure completed at Day 1 are considered study participants. The following subject populations are defined to assess the safety and efficacy of AG-920 in comparison with placebo.

### Safety Population

The safety population is defined as all subjects who are randomized and who have received at least one drop of the dose (2 drops) of the study medication. The safety population will be utilized for comparative safety analyses among treatment groups.

### Intention-to-treat (ITT) Population

This population is defined as all subjects who are randomized to treatment and have received at least one dose (two drops) of the study medication. The ITT population is the primary population for efficacy evaluation in this study. Treatment identification is defined in the ITT population by treatment assignment. The ITT population will be identified and finalized before the database is locked and the study is unmasked.

### Per-Protocol (PP) Population

This population is defined as sub-population of the ITT population. The PP population is the secondary population for efficacy evaluation in this study and will be defined as all randomized subjects who completed the study treatment with no major protocol violations likely to seriously affect the primary outcome of the study as judged by a masked evaluation prior to the unmasking of the study treatment. In case there is a difference between treatment assigned and received, treatment actually received will be utilized to define the treatment identification in the PP population. In case there are missing data in efficacy measures, the analysis of the PP population will be based on observed or actual data only (without imputation). The PP population will be identified and finalized before the database is locked and the study is unmasked.

## **3.2 Screening and Enrollment**

A screening summary including the number of subjects screened for study participation will be presented by site (Table 1.1.1).

An enrollment summary including the number of subjects enrolled, randomized, and completed the study will be presented for all enrolled subjects and by site (Table 1.1.2). Enrolled subjects include those individuals who are screened and returned to the clinic on Day 1 and randomized into the study. The number of subjects treated with at least one drop of the dose (2 drops) of the study medication (i.e., the safety population) will be summarized for each treatment group and overall (Table 1.1.3). The number of subjects treated with at least one dose (2 drops) of the study medication (i.e., the ITT population) will be summarized for each treatment group and overall (Table 1.1.4). The number of subjects in the PP population will be summarized for each treatment group and overall (Table 1.1.5).

## **3.3 Population Demography**

For subjects enrolled, safety, ITT, and PP populations, descriptive summaries of demography and baseline characteristics will be presented for each subject group and overall to establish baseline comparability (Tables 1.2.1 to 1.2.4).

Demography includes age in years (continuous and categorical 18 to 29, 30 to 39, 40 to 49, 50 to 64, and 65+), gender, race, ethnicity, weight, and height. Demography will also be listed for all subjects enrolled (Listing 1).

### **3.4 Disease Characteristics and Prior Treatment**

For the safety, ITT and PP population, descriptive summaries of baseline study eye characteristics will be presented for each treatment group and overall to establish baseline comparability (Tables 1.3.1 to 1.3.3).

BCVA and other characteristics of the study and non-study eye will be listed for all subjects enrolled (Listing 1).

### **3.5 Medical History**

Medical history will be listed in listing and CRF data tabulation.

### **3.6 Disposition of Study Participants**

Subject disposition including completion and discontinuation along with CRF-based termination reason will be summarized for safety and ITT populations (Tables 1.4.1 to 1.4.2). Subjects' early termination details will be listed for all subjects enrolled (Listing 2).

Subjects' randomized treatment, randomization (or kit) number, and randomization date as well as actual treatment received will be listed for all subjects randomized (Listing 3).

### **3.7 Protocol Deviations and Violations**

A summary of protocol deviation and violations will be provided for ITT population (Table 1.5.1). Subjects who are randomized to receive double-masked treatment in the study and included in the ITT population, but do not have two drops dosed and/or post-dose status of pinch pain assessment will be listed for subjects randomized (Listing 4).

Subjects who are included in the ITT population, but not included in the PP population due to either protocol violations or other reasons will be listed for all subjects excluded from the PP population (Listing 5).

## **4 EFFICACY EVALUATION**

### **4.1 Datasets Analyzed**

The ITT population is defined as the primary efficacy population, and the PP population as the secondary efficacy population. Both populations will be identified and finalized before the database is locked and the study is unblinded. The definitions of the two populations are provided in Section 3.1.

In addition, sub-population datasets may be defined as the ITT subjects in each gender group (male vs. female), each age group (18-34 vs. 35+), each racial group (Caucasian vs. Non-Caucasian), and each color of the eye iris (dark brown vs. other colors).

### **4.2 Treatment Compliance**

The compliance rate during treatment will be summarized by treatment group and demographic parameters for the safety and ITT populations (Tables 1.5.2 and 1.5.3).

#### **4.3 Data Missing and Imputation**

A summary of the observed data missing and imputation performed will be reported for study eye anesthetic response status, the primary efficacy measure, of the ITT population in Table 1.6.1.

#### **4.4 Baseline Measures**

As the participants of this study are normal subjects, rather than patients, there is no prior medical condition involved in this study. Descriptive statistics of the study eye characteristics are presented in Section 3.4.

#### **4.5 Efficacy Results and Tabulations**

##### **4.5.1 Results of primary efficacy analysis**

Descriptive and inferential statistics on the ITT population of the proportion of subjects with anesthetic response at 5 minutes post dose will be presented in Table 2.1.1.

For the PP population, the results of the same proportion analysis on the number of subjects with anesthetic response at 5 minutes post dose will be presented in Table 2.1.2.

The by-site summary of descriptive statistics of the number of subjects with anesthetic response at 5 minutes post dose will be presented in Table 2.1.3.

The results of the proportion analysis on the number of subjects with anesthetic response at 5 minutes post dose will be presented for the sub-populations of men vs. women in Tables 2.2.1 and 2.2.2; for 34 years or younger vs. 35 years or older in Tables 2.2.3 and 2.2.4; for Caucasian vs. Non-Caucasian in Tables 2.2.5 and 2.2.6; and, for iris color dark brown vs. other colors in Tables 2.2.7 and 2.2.8.

Individual subjects' primary efficacy data (i.e., pinch pain response) assessed post dose on Day 1 by Investigator, with and without imputation, will be listed by treatment for the ITT population (Listing 6).

